the effects of fermented vegetables on the composition of the gut microflora and other biological and clinical parameters associated with obesity and other chronic diseases.

Study Aims

Aim 1: To examine the effect of daily consumption of fermented vegetables compared with non-fermented vegetables for 6 weeks on markers of metabolic syndrome and inflammation of overweight and obese women.

Hypothesis 1: Consumption of fermented vegetables will improve markers of metabolic syndrome (blood pressure, insulin, adiposity) and inflammation, such as C-reactive protein (CRP), and lipopolysaccharide (LPS) in overweight and obese women.

Aim 2: To examine the effect of daily consumption of fermented vegetables compared with non-fermented vegetables for 6 weeks on the profile of the gut microflora.

Hypothesis 2: Consumption of fermented vegetables will lead to a shift in microbial communities towards an increase in communities regarded as probiotics such as Bifidobacteria and Lactobacilli.

Significance

Obesity continues to be a major public health burden and its consequences have a significant impact on disease risk and quality of life, particularly in women who are more affected by this problem than men. Several weight loss interventions have been tested in the past 30 years, but it does not seem that a great impact in obesity treatment has been made so far. This is partially due to the fact that weight loss trials have a transient positive effect, which gets reversed as soon as the intervention stops. Due to these challenges faced by traditional weight loss trials, there is a need to look for alternative approaches to reduce the burden of obesity, particularly in women. Although it is now well recognized that there is a

strong relationship between the gut bacteria and obesity, there is a lack of feeding studies aimed at altering the composition of the gut bacteria via consumption of fermented foods. In addition, most of the studies examining the effects of fermented foods on health and disease parameters have been conducted in Asian countries, where the consumption of fermented foods like kimchi and soy products is high compared with Western countries. This proposal addresses the gap in the research with fermented foods that exists in the U.S. by examining the effects of consumption of fermented vegetables on several markers associated with obesity in women.

Methodology and analysis

Methodology

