Study design: This will be a parallel arm study where 39 women will be randomized into one of three treatment groups: a fermented vegetable group (n=13), a non-fermented vegetable group (n=13), and a control group (n=13). The duration of the study will be 6 weeks and women in the vegetables groups will be asked to consume 1 cup of vegetables (140 g) per day for the entire duration of the study as well as follow their usual diet. Women randomized into the control group will be asked to follow their usual diet. Biological samples including feces and blood samples will be collected at baseline, before randomization and at the end of the 6-week intervention.

Study participants: Thirty-nine overweight and obese women aged 20-59 years will be recruited for this study. The table below shows inclusion and exclusion criteria for the study:

INCLUSION CRITERIA	EXCLUSION CRITERIA
BMI: 26-40 kg/m ²	BMI < 26 kg/m ²
Non-smoker	Smoker

No previous diagnosis of cancer	Taking medications that affect appetite or body weight
No thyroid disease	Uncontrolled Hypertension
No diabetes	Diabetes
Willing to consume 1 cup of vegetables daily for 6 weeks	Not willing to consume 1 cup of vegetables daily for 6 weeks
No use of psychotic or depression medication	Willing to show up at two appointments
No medication to lose weight	Following a fad diet
Not on a weight loss diet	Using antibiotics frequently
No use of antibiotics over the past 3 months	Diagnosed with autoimmune disease, like psoriasis, rheumatoid arthritis, thyroid disease, colitis
No consumption of fermented vegetables on a regular basis	Regular consumption of fermented vegetables
No history of autoimmune disease, including gastrointestinal disease	

Study procedures: Participants will be recruited by posting flyers at UNF Women's Center and in Jacksonville Women's clinics, as well as by newspaper advertisements. Interested participants will be asked to contact the study via email sent to an email account that will be created for the study. Upon receiving emails from interested participants, study staff will conduct a screening interview to ensure eligibility for the study. If women are found to be eligible after the initial screening interview, a screening clinic visit for verification of eligibility status will be scheduled. At the screening clinic visit all the study

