Survey data collection: Participants will be asked to fill out several surveys to assess food intake, demographics, and prescription medication intake. The diet history questionnaire, which is a 120-item food frequency questionnaire designed by the National Cancer Institute [15] will be used to assess baseline and follow-up dietary intake of participants. Participants will also receive daily logs to monitor gastrointestinal function (frequency of defecation and consistency of stools) and possible side effects of consumption of fermented vegetables such as bloating, diarrhea, constipation, and headache.

Clinical data collection: Height will be measured in centimeters using a Detecto 439 Eye Level Beam Physician Scale 400lb x 4oz with Height Rod. Weight and %body fat will be obtained via Bioimpedance (Tanita BC-532). Sagittal abdominal diameter (a measure of visceral obesity) will be assessed using a Holtain-Kahn caliper. Blood pressure will be measured using a Digital blood pressure monitor (Omron HEM907XL).

Compliance: To assess compliance in the vegetables groups, participants will be asked to fill out logs where they will check whether they consumed the vegetables for the day or not. Participants will also be asked not to discard any vegetables that have not been consumed. These containers will be picked up weekly at the time participants receive their following week's supply. This will allow us to quantify the amount of vegetables that is truly consumed by the participants every week.

Microflora analysis: Stool samples will be stored at -70C until DNA extraction. DNA will be extracted using the QIAamp DNA stool mini kit (Qiagen, Hilden, Germany) and samples will be stored until analysis of microflora. Analysis of microflora in stool samples and vegetables samples will be conducted

in the laboratory of [name] at St. Cloud State University. This type of analysis is currently not being performed at UNF, therefore, [name] will be working on a contract to have the samples measured at St. Cloud State University. Drs. [name] and [name] have had a working relationship since 2012 when they worked on a study related to fermented wheat bran and its effects on the composition of the gut microflora at the University of Minnesota.

Analysis

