Treatment groups will be compared at both times points using analysis of variance. Changes from baseline within treatment groups in clinical and laboratory measures will be compared by paired *t* tests. Pearson's correlation coefficients will also be calculated between clinical and laboratory parameters and alterations in the intestinal microflora.

Plan for dissemination of results

The findings from this project will be disseminated in three different ways: via open access peer-reviewed manuscripts, poster presentations at scientific meetings, and via UNF newspaper. It is also expected that this project will originate pilot data to apply for external funding from institutions such as the Obesity Society and the American Heart Association.

Timeline

Project activities	Year 1				Year 2			
	Q1	Q2	Q3	Q4	Q1	Q2	Q3	Q4
IRB application and approval								
Recruitment and enrollment of participants								
Intervention/data collection								

Sample preparation for analysis and shipping							
Intestinal microflora analysis at St. Could State University							
Statistical analysis							
Manuscript preparation and dissemination							

Project budget (\$14,975.65)

Undergraduate research assistant (\$1,431.75)

I am requesting funds to hire an undergraduate student for 7 hours per week to help with recruitment and the intervention for 19 weeks at \$10/hr. ($\$10 * 19 * 8 = \$1330 + 7.65\% = \$1,431.75$).

Graduate student (nurse practitioner) (\$280)

I would like to hire nurse practitioner students for the blood draws. I estimate that each blood draw will take 15 minutes, which adds up to 10 hours for 39 participants before and 10 hours after the intervention for a total of 20 hours. ($\$13/h for 20 hours = \$260 + 7.65\% = \$280$)

Laboratory supplies

Assay kits for assessment of blood markers (\$2,362)

CRP: 1 kit for 36 samples at \$479, need 2 kits = \$958, Insulin: 1 kit for 36 samples at \$449, need 2 kits = \$898, LPS: 1 kit for 36 samples at \$253, need 2 kits - \$506

Blood and stool collection supplies (\$433)

Needles, tubes, tourniquets: \$150, Tubes to store serum in ultracold freezer: \$159, Stool collections cups and hats: \$108, Tongue depressors: \$16

Microflora analysis (\$8,500)

DNA extraction of stool samples: \$900

Sequencing for identification of microflora \$1,500 per 17 samples, we will have a total of 84 samples: \$7,500

Shipping (overnight) of stool samples to Minnesota: \$100

Vegetables (\$900)

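### Hypothesis 2 targets Bifidobacteria and Lactobacilli, yet probiotic supplements are not named in eligibility or surveys, and the between-arm comparison leaves the baseline stool value unused

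*Combined protocol and SAP*

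**What the plan says.** Under Study Aims, Hypothesis 2 expects fermented vegetables to produce "an increase in communities regarded as probiotics such as Bifidobacteria and Lactobacilli".

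The inclusion and exclusion table under Study participants protects that outcome in two ways: "No consumption of fermented vegetables on a regular basis" and "No use of antibiotics over the past 3 months". No row mentions probiotic supplements. Under Study design, participants are asked to keep to their usual diet; supplements are not mentioned there.

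Survey data collection lists "several surveys to assess food intake, demographics, and prescription medication intake". Diet at baseline and follow-up is measured with a "120-item food frequency questionnaire designed by the National Cancer Institute", whose items are not shown.

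Blood and stool samples are "collected at baseline, before randomization and at the end of the 6-week intervention", so a pre-randomisation stool value will exist for each woman.

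Under Analysis, "Treatment groups will be compared at both times points using analysis of variance". Change from baseline enters in two other places. One is within arms: "Changes from baseline within treatment groups in clinical and laboratory measures will be compared by paired" *t* tests. The other is correlations between clinical or laboratory parameters and microflora alterations. No between-arm analysis is stated to use baseline.

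**The concern.** The protocol's contrast is vegetables fermented by live bacteria against vegetables without live organisms. Probiotic supplements may contain the same organisms that Hypothesis 2 measures, so a woman who takes them may have a shifted stool profile whatever her arm. The protocol already screens on regular fermented-vegetable intake and on antibiotics, so the omission leaves a gap in its own approach.

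With 13 women per arm, a few users can widen the spread or fall unevenly between arms. An ANOVA of week-6 values carries all of that variation into the comparison, although a baseline value that would absorb much of it is already in hand. Supplements started after randomisation are a separate matter: baseline cannot correct for them, and without a record of use nobody could examine them.

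**Working it through.** **The plan's own figure.** The sample size is 3 × 13 = 39, which agrees. No power, effect size, SD or alpha is given, so nothing further can be reproduced.

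**Assumptions (none is in the documents).** Two-sided 5% test of one pair of arms. Benchmark of 80% power, chosen for illustration. A share p of women use supplements, equally likely in every arm, and their outcome is shifted by k SD, where SD is the SD among non-users. The correlation between visits among non-users is r. Errors are roughly normal on the analysis scale.

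**Step 1: benchmark.** Noncentral t, n = 13 per arm, df 24: detectable difference 1.145 SD. Pooling the error over three arms (df 36) gives 1.13 SD, a minor change.

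**Step 2: unadjusted week-6 comparison.** The variance becomes 1 + q, with q = p(1 − p)k². Power is evaluated at 1.145/√(1 + q). For p = 0.10 and k = 1, q = 0.09, √1.09 = 1.044, and power is 76.5%.

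| Users | k = 0.5 | k = 1 | k = 2 |
|---|---|---|---|
| 5% | 79.5% | 78.2% | 72.9% |
| 10% | 79.1% | 76.5% | 67.1% |
| 20% | 78.4% | 73.9% | 59.0% |
| 30% | 78.0% | 72.2% | 54.2% |

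Up to k = 1 the largest loss is 80 − 72.2 = 7.8 points. At k = 2 the loss is 7 to 26 points. Simulating the user mixture gave matching power, and a type I error of 0.047–0.051 for shifts of 1 to 3 SD, so use that is unrelated to arm does not create false positives. The chance that two arms differ by two or more users is 16%, 31% and 46% at 5%, 10% and 20% use.

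**Step 3: week 6 with the baseline stool value as covariate, stable users kept.** The residual variance is (1 + q) − (r + q)²/(1 + q), and the detectable difference (df 23) is 1.148 times its square root. Without users this is 1.148 × √(1 − r²); at r = 0.5, 1.148 × 0.866 = 0.99. For p = 0.30, k = 2, r = 0.5: q = 0.84, the residual variance is 1.84 − 1.34²/1.84 = 0.864, and the result is 1.07. The same cell unadjusted is 1.145 × √1.84 = 1.55.

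| r | No users | Users kept, whole grid |
|---|---|---|
| 0.3 | 1.09 SD | 1.10–1.22 SD |
| 0.5 | 0.99 SD | 1.00–1.07 SD |
| 0.7 | 0.82 SD | 0.82–0.85 SD |

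At r = 0.5, excluding users after adjustment improves the detectable difference by at most 1.07/0.99 − 1, about 7%, and by under 3% for k up to 1.

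These adjusted figures leave out the average cost of chance baseline imbalance, a factor of √(1 + 1/22) = 1.022 with 26 women, so they are about 2% optimistic.

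**Step 4: supplements started mid-study.** If a share s starts equally in all arms, q = s(1 − s)k² affects week 6 only. With the covariate, the detectable difference grows by √(1 + q/(1 − r²)) − 1. At r = 0.5 and s = 5–10%, this is 0.8–1.5% at k = 0.5, 3.1–5.8% at k = 1 and 12.0–21.7% at k = 2.

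**Step 5: recruitment if users are excluded.** 39/(1 − p) is 41.1, 43.3, 48.75 and 55.7, that is 42, 44, 49 and 56 otherwise-eligible women at 5%, 10%, 20% and 30% use.

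**The case against.** The strongest reply is that no consequence is documented. Prevalence, shift, correlation and the 80% benchmark are all the reviewer's, and the trial is partly meant to produce pilot data. This stands: the figures show how the loss behaves, not how large it is here.

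Supplement use may be captured already. The contents of the screening interview and of the questionnaire are not shown, so the documents do not support saying that use goes unrecorded; they support only that it is not named. The planned baseline ANOVA would also display a chance imbalance in the stool outcome, though displaying it does not correct the week-6 comparison.

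Most of the gain comes from baseline adjustment, which would be sensible with no users at all. That also stands, and it is why adjustment is the main fix. Exclusion costs most where use is commonest, and it draws a line that the protocol leaves loose elsewhere: its Significance section counts soy products among fermented foods, yet only fermented vegetables are restricted.

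A reader might infer systematic bias. The documents do not support that for existing use, since allocation is randomised. Starting after allocation could differ by arm, because no blinding is described, but nothing in the documents shows that it does. A reader might also infer that the noise matters only when use is common and its effect large. The table contradicts this: 5% use with a 2 SD shift already gives 72.9% power. The two act jointly.

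**Conclusion.** The omission is real and minor. Probiotic supplements are not named in the eligibility table or the stated survey content, and the between-arm analysis does not use the baseline stool value. The effect of existing use is lost precision and chance imbalance.

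Its size cannot be fixed from the documents. Under the stated assumptions it is at most 8 power points for shifts up to 1 SD and use up to 30%, and larger at 2 SD. Baseline adjustment recovers most of it for stable users. How much depends on the visit correlation: at 0.5, keeping users and adjusting does better than excluding them without adjusting (1.00–1.07 against 1.15 SD), but at 0.3 the adjusted range of 1.10–1.22 SD straddles 1.15, so adjustment alone does not always beat exclusion. This is a point to consider, not a threat to validity.

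**What to change.** 1. **Main change.** In Analysis, state that the arms will be compared at week 6 by ANCOVA with the baseline stool value as covariate, in place of the unadjusted week-6 ANOVA. It needs no new sample, assay or visit, and uses one degree of freedom.

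2. **Supporting change.** Ask all three arms not to start probiotic supplements during the 6 weeks, and add a question on their use at both visits. The cost is one instruction and one survey item. It covers what baseline adjustment cannot, including any difference between arms in starting.

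3. **Optional.** Exclude women who used probiotic supplements in the past 3 months, matching the antibiotic look-back. This costs a screening question and a pool of about 42–56 otherwise-eligible women at 5–30% use, and adds little once baseline is in the model. If recruitment is slow, record use and keep these women.

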procedures will be explained in detail, and participants will be asked to sign the consent form if they agree to participate. Blood and stool samples will be collected and once all eligibility criteria are confirmed, participants will be randomized into one of the three groups and arrangements will be made for weekly pick up/delivery of vegetables to those in the vegetables groups.

Vegetables preparation: Fermented vegetables for the entire study will be provided by a local producer weekly, whereas non-fermented vegetables samples will be obtained at a local grocery store. The process of vegetable fermentation involves *Lactobacilli* and *Bifidobacteria* that are naturally found on the leaves of cabbage, carrots and on cucumbers. These bacteria are able to convert the carbohydrates present in these vegetables into lactic acid under anaerobic conditions. The lactic acid is responsible for the acidic flavor of the fermented vegetables. The non-fermented vegetables will serve as a positive control for the fermented vegetable group, because it will have a similar flavor but no live microorganisms, mainly because store-bought pickled vegetables and sauerkraut are made by a different process that uses acetic acid, instead of live bacteria. Vegetable samples will be portioned by study staff using food safety precautions and delivered to participants weekly.

Biological sample collection: Blood samples will be collected in red top tubes to obtain serum for determination of insulin, CRP, and LPS. CRP will be measured using a commercial ELISA kit (Cat#DCRP00, R&D Systems, Minneapolis, MN). LPS will be measured using Pierce LAL chromogenic endotoxin quantitation kit (Cat#88282, ThermoFisher Scientific, Waltham, MA). All analyses will be conducted in [name] laboratory, which is already set up for these measurements. Stool samples will be collected to analyze the composition of the gut bacteria. Participants will receive a stool collection kit prior to the initial screening visit and they will be asked to bring the stool sample to the screening visit.

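### CRP is drawn once per visit with no check for acute illness; in an arm of 13, one ill woman can cancel or reverse a moderate diet effect on CRP and remove most of the power to see it

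*Combined protocol and SAP*

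**What the plan says.** The protocol and analysis plan are one document. Under Study Aims, Hypothesis 1 names CRP as a marker of inflammation: "Consumption of fermented vegetables will improve markers of metabolic syndrome (blood pressure, insulin, adiposity) and inflammation, such as C-reactive protein (CRP". No expected size of effect and no SD are given.

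On timing, the Study design paragraph states: "Biological samples including feces and blood samples will be collected at baseline, before randomization and at the end of the 6-week intervention". The budget confirms a single draw per woman at each time: "each blood draw will take 15 minutes, which adds up to 10 hours for 39 participants before and 10 hours after the intervention". The same serum serves three assays: "Blood samples will be collected in red top tubes to obtain serum for determination of insulin, CRP, and LPS".

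The nearest safeguards are elsewhere. The eligibility table excludes chronic inflammatory disease ("Diagnosed with autoimmune disease, like psoriasis, rheumatoid arthritis, thyroid disease, colitis") and requires no antibiotics in the preceding 3 months. The surveys record prescription medication, and the daily logs record bowel function and possible side effects. None of these is linked to the CRP sample.

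The Analysis section says "Treatment groups will be compared at both times points using analysis of variance" and adds paired t tests of change within arms. It gives no transformation, outlier rule or sensitivity analysis.

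**The concern.** Aim 1 is about the persistent inflammation that accompanies overweight. CRP also rises for a short time with a cold, a dental or urinary infection, an injury or a vaccination, and then falls again. A woman who is ill on the day of a draw is sampled and analysed as though her value reflected her diet.

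With 13 women per arm and tests built on arithmetic means, one such value carries a lot of weight. At week 6 in the fermented-vegetable arm it can hide a real benefit. At baseline, or in a comparator arm at week 6, it makes the estimate look better than it should. The project is meant to supply pilot data for funding applications, so a distorted CRP estimate or SD would carry into the next study's design. Illness status at the draw cannot be recovered later if nobody asked.

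**Working it through.** **Inputs from the document.** Three arms of 13, so 39 women. Two draws each, so 39 × 2 = 78 samples. ANOVA at each time point and paired t tests within arms. The document gives no CRP mean, SD, effect size, alpha or power, so there is no figure of its own to reproduce.

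**Assumptions.** Usual CRP is log-normal with median 3 mg/L and log-SD 1. The correlation of log values between visits is 0.8. One woman has 20, 40 or 80 mg/L at one visit. Tests are two-sided at 0.05.

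**Shift in the arm mean.** The usual mean is m = 3 × exp(0.5) = 4.95. One value x shifts the mean of 13 by (x − m)/13:

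- x = 20: (20 − 4.95)/13 = 1.16 mg/L
- x = 40: (40 − 4.95)/13 = 2.70 mg/L
- x = 80: (80 − 4.95)/13 = 5.77 mg/L

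**Size of diet effect that this cancels.** Suppose the diet lowers CRP by a fraction r. Twelve women average (1 − r)m and one has x, so the arm mean is back at m when x = m(1 + 12r):

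- r = 20%: 4.95 × 3.4 = 16.8 mg/L
- r = 30%: 4.95 × 4.6 = 22.8 mg/L
- r = 50%: 4.95 × 7 = 34.6 mg/L
- r = 100%: 4.95 × 13 = 64 mg/L. If the shift is instead measured from the untreated mean, the figure is 14m = 69 mg/L.

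**Spread.** In simulated arms, one value of 40 mg/L raises the median SD of change from 3.36 to 10.80 mg/L.

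**Chance of a significant benefit, one woman ill at week 6** (simulated arms of 13, paired t test):

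| True fall, scale | None ill | 20 mg/L | 40 mg/L |
|---|---|---|---|
| 30%, raw | 25% | about 1% | 0.1% |
| 50%, raw | 68% | 3% | 0.3% |
| 50%, log | 95% | 38% | 20% |

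With a true 30% fall, a value of 40 mg/L turns the average change from −1.5 to +1.3 mg/L.

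**Other assumptions.** With log-SD 0.9, correlation 0.7 and one woman raised by 20 mg/L at week 6, a true 30% fall gives an average difference between two arms of +0.19 mg/L instead of −1.37.

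**Illness at baseline, no true effect.** The raw paired t test shows a significant benefit in about 1.5% of arms when nobody is ill and about 1.5% at 20 mg/L. At 40 mg/L the rate is no more than 0.2%, and at 80 mg/L it is 0%. The outlier moves the mean but inflates the SD as well.

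**How often.** If 2% to 10% of women are acutely ill at a visit (assumed), the chance of at least one in an arm of 13 is 1 − 0.98^13 = 23% to 1 − 0.90^13 = 75%.

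**The case against.** A reader might infer that one illness can outweigh any diet effect. The documents state no effect to compare with, and on these assumptions that would take a value of roughly 64 to 69 mg/L. Milder illness cancels only moderate effects.

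A reader might also infer that recovery from a baseline illness produces spurious significant improvement, or that the trial is biased. Neither is supported. The baseline outlier distorts the within-arm estimate without raising the rate of false significant benefit in the planned raw-scale test. Baseline blood is drawn before randomisation, and illness unrelated to diet falls on the arms by chance.

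Three further objections stand in part:

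- The antibiotic criterion screens out some recent infections. It acts at entry only, and it misses viral illness, injury and vaccination.
- The screening interview is not itemised, so the absence of a question is read from silence. Even so, no rule links any answer to the draw or the analysis.
- The illness rate and the CRP levels are assumptions, and not every ill woman would reach 20 mg/L. Across all 39 women the chance of at least one being ill at a visit is 55% to 98%, but the influence on an arm's mean depends on the per-arm chance of 23% to 75%.

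The log scale is a strong partial answer: one value of 40 mg/L multiplies the geometric mean by only (40/3)^(1/13) = 1.22. The plan does not specify it, and the table shows that it does not restore the lost power.

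**Conclusion.** The gap is real and worth closing. Under the plan as written, one acutely ill woman at week 6 can cancel or reverse the estimate of a moderate CRP effect in her arm and take most of the power with it. At baseline the harm is a distorted within-arm estimate and an inflated SD. The sizes depend on the assumed CRP distribution and illness levels, but both sets of assumptions tried give the same pattern. The result does not extend to LPS, which was not calculated, and it is not evidence of systematic bias between arms.

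**What to change.** 1. Before each draw, ask about recent fever, infection, injury, dental work and vaccination, over a look-back period fixed in the protocol.
2. If the answer is yes, defer the research draw. At baseline, take it later but still before randomisation. At week 6, take it within a short fixed window, and state what the study diet arrangement is for those days. The budget has containers for 42 days. Its 223 oz per person is about 6,322 g (28.35 g per oz), or 45 days at 140 g, so supply as well as timing must be addressed.
3. Flag any sample that cannot be deferred.
4. Analyse CRP on the log scale, adjusted for baseline.
5. Prespecify a sensitivity analysis that leaves out samples flagged by the questions. Do not drop all values above a CRP cut-off: under the assumed distribution about 11% of healthy values exceed 10 mg/L, and removing high week-6 values selects on the outcome after randomisation.

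The cost is a short question list at two existing visits, a few rebooked or late draws and one extra analysis. Deferral replaces a sample and so needs no extra assays. Repeat samples would need them, and the budget ("CRP: 1 kit for 36 samples", two kits) covers 72 samples against the 78 planned.

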lower ratio of *Firmicutes* to *Bacteroidetes*, which are some of the most abundant bacterial phyla present in the human gut [8]. Some studies suggest that the altered intestinal microflora profile of obese individuals may lead to an increase in production of lipopolysaccharide (LPS) endotoxin, which is derived from the cell wall of gram-negative bacteria in the gut (such as the *Bacteroidetes* mentioned earlier) and induces an inflammatory response by the body [9]. This may be one reason why overweight and obese individuals often present elevated levels of inflammatory markers in the blood, including LPS [10] and other more established markers of inflammation such as C-reactive protein (CRP) [11].

The composition of the intestinal bacteria is influenced by several factors, including host genotype, age, sex, antibiotic/medication use, disease, and diet. Changes in the intake of specific food components may lead not only to changes in the gut bacteria but may also lead to changes in gene expression of different tissues in the host, which may be directly related to more or less fat storage [12]. For example, a cross-over study looking at the effects of consumption of 4 weeks of fermented kimchi and 4 weeks of fresh kimchi in obese Korean subjects (7 male and 15 female) found significant decreases in body weight, and body fat after consumption of fermented and fresh kimchi. In addition, decreases in blood pressure, percent body fat, fasting glucose, and total cholesterol were significantly greater during the fermented kimchi phase compared with the fresh kimchi phase [13]. In a parallel arm study conducted with overweight and obese Korean women, consumption of both fermented and fresh kimchi resulted in a decrease in the *Firmicutes* to *Bacteroidetes* ratio and in the relative abundance of *Bifidobacteria*, even though there were no significant differences between groups in body weight or inflammatory markers [14]. The findings from these Korean studies suggest that fresh and fermented kimchi may have different effects on intestinal bacteria and metabolism of the host. Unfortunately, very few studies examining the effects of fermented foods on metabolic parameters have been conducted in the U.S., likely due to the low consumption of fermented vegetables by the population. The present study was designed to investigate

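### Both aims compare fermented with non-fermented vegetables, but the only between-arm test of effect is a three-group ANOVA at week 6, with no contrast, estimate or baseline adjustment stated

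*Combined protocol and SAP*

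**What the plan says.** The question is stated twice under Study Aims. Aim 1 is "To examine the effect of daily consumption of fermented vegetables compared with non-fermented vegetables for 6 weeks on markers of metabolic syndrome", with inflammatory markers added; Aim 2 is "To examine the effect of daily consumption of fermented vegetables compared with non-fermented vegetables for 6 weeks on the profile of the gut microflora". The Vegetables preparation paragraph gives the comparator the matching role: "The non-fermented vegetables will serve as a positive control for the fermented vegetable group". A third arm, on usual diet, is also randomised, with 13 women planned in each arm (Study design).

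The Analysis section has three sentences. The first gives the between-arm method: "Treatment groups will be compared at both times points using analysis of variance". The second stays within each arm and uses t tests: "Changes from baseline within treatment groups in clinical and laboratory measures will be compared by paired". In the third, Pearson correlations relate clinical and laboratory parameters to microflora changes. No other part of the document names a pairwise contrast, a follow-up test, a between-arm difference with a confidence interval, a baseline covariate, or a between-arm comparison of change. Baseline is compared between arms, but only in an ANOVA of its own.

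**The concern.** The baseline ANOVA precedes treatment and the correlations do not compare arms. The paired tests look at one arm at a time. That leaves the week-6 ANOVA as the only between-arm test of effect, and its F test asks whether three means differ in any way. A significant result could reflect fermentation, or simply eating either kind of vegetable every day.

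The plan's own background keeps both possibilities open. The cross-over kimchi study "found significant decreases in body weight, and body fat after consumption of fermented and fresh kimchi", while falls in some other measures were "significantly greater during the fermented kimchi phase compared with the fresh kimchi phase".

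The dissemination section expects that "this project will originate pilot data to apply for external funding". For these aims, what such data should supply is the fermented minus non-fermented difference and its uncertainty. The plan does not say that either will be reported.

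**Working it through.** **Inputs.** From the documents: three arms of 13, and 3 × 13 = 39, which agrees with the stated total. The plan gives no power calculation to reproduce. Assumed, because the documents give none of these: normal outcomes, a common SD (set to 1), two-sided α = 0.05, and 13 completers per arm unless stated. The baseline to week-6 correlation r is varied.

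**1. What the F test can distinguish.** Power follows the noncentral F(2, 3n − 3) with λ = n × Σ(mean − grand mean)².
- Only the fermented arm shifts by d: Σ = (2d/3)² + 2(d/3)² = 2d²/3.
- Both vegetable arms shift by d: Σ = 2(d/3)² + (2d/3)² = 2d²/3.

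The two values of λ are identical (13 × 2/3 = 8.67 at d = 1), so the power is identical.

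**2. Power for the comparison the aims name.** The named contrast uses the noncentral t with 36 df and noncentrality d√(n/2). The F-gated t test (run only if F is significant) and Tukey were simulated, 400,000 trials per setting, with only the fermented arm shifted.

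| d (SD) | F test, either pattern | Named contrast | F-gated t | Tukey |
|---|---|---|---|---|
| 0.4 | 16% | 17% | 11% | 9% |
| 0.6 | 31% | 32% | 24% | 19% |
| 0.8 | 51% | 51% | 42% | 35% |
| 1.0 | 72% | 70% | 63% | 55% |

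When both vegetable arms shift equally, the last three procedures falsely find a fermented versus non-fermented difference in 5%, 3–5% and 2% of trials. The F test still rejects at the rates in its column.

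**3. Baseline adjustment.** ANCOVA multiplies the error variance by 1 − r² and uses 35 df. Estimating the baseline slope costs a further factor of about √(1 + 1/34). The difference detectable with 80% power and the mean 95% CI half-width (60,000 simulated trials per setting), in SD units, are:

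| | Unadjusted | r = 0 | 0.3 | 0.5 | 0.7 | 0.8 |
|---|---|---|---|---|---|---|
| Detectable difference | 1.13 | 1.15 | 1.09 | 0.99 | 0.82 | 0.69 |
| CI half-width | 0.79 | 0.80 | 0.77 | 0.69 | 0.57 | 0.48 |

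**4. Why paired tests cannot substitute.** If both vegetable arms truly change by the same amount, and each paired test (12 df) has power p, exactly one is significant with probability 2p(1 − p). At changes of 0.3, 0.5, 0.6 and 0.8 within-person SD, p = 0.169, 0.382, 0.512 and 0.754, which gives 28%, 47%, 50% and 37%.

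**5. Sensitivity to completers.** The budget allows for dropout, and its mileage line counts 28 women in the vegetable groups (14 per arm), against 26 under the stated design. The 10-per-arm case is illustrative. At 1.0 SD:

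| Per arm | F test | Contrast | F-gated t | Tukey | Detectable difference, unadjusted |
|---|---|---|---|---|---|
| 10 | 58% | 58% | 50% | 42% | 1.30 SD |
| 14 | 75% | 73% | 67% | 59% | 1.09 SD |

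**The case against.** The strongest reply is that pairwise follow-up after ANOVA is routine and the text does not exclude it. Follow-up would separate the two patterns. On that reading the loss from an F-gated t test is only about 6 to 9 percentage points across the effect sizes shown, and nothing in the documents points to 1.0 SD as the relevant one. The Tukey comparison is also not like for like: Tukey controls error over all three pairs, whereas three unadjusted pairwise tests have a familywise error of about 12% when no arm differs. These points stand, and they limit the size of the harm. But no follow-up is written, so its form could be chosen after the data are seen, and even then no estimate is promised.

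Baseline adjustment is a matter of efficiency. Comparing week-6 values in a randomised trial is valid, the gain is small at r = 0.3, and at r = 0 there is a slight loss. This stands too.

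Hypotheses 1 and 2 name no comparator, which may explain the within-arm tests. Both aims do name one, however, and the non-fermented arm is there to serve it. The plan does not propose comparing paired-test results across arms; step 4 shows only what would follow if readers did so.

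The normal, equal-variance assumption is least comfortable for the microflora measures of Aim 2. The planned ANOVA and paired t tests rest on comparable assumptions.

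**Conclusion.** The concern holds and should be fixed. Followed as written, the analysis contains no test or estimate of the comparison that both aims name. That conclusion needs no assumed SD, correlation or effect size: it follows from the text and from the equality of the two noncentrality parameters.

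The cost in power does depend on the assumptions. If follow-up testing were used, the loss relative to a named contrast would be about 6 to 9 points (F-gated) or 8 to 16 points (Tukey, with the familywise caveat) between 0.4 and 1.0 SD. The benefit of baseline adjustment runs from negligible at low correlation to a fall of roughly 0.4 SD in detectable difference at r = 0.8. Confidence is high on the omission and lower on the size of its consequences.

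**What to change.** Rewrite the first two sentences of the Analysis section:

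- For each marker, fit an ANCOVA of the week-6 value on arm (three levels) and that marker's baseline value.
- Name in advance the adjusted fermented minus non-fermented difference, with its 95% CI, as the test of the aim. Make the comparisons with control secondary, and say whether they are adjusted for multiplicity.
- Report baseline values and within-arm changes descriptively.

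If baseline adjustment is not wanted, the same contrast and CI on week-6 values still answers the aims. Choosing a primary marker, and a scale for skewed markers, is a separate matter.

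The cost is one degree of freedom (36 to 35). At worst, with zero correlation, that adds about 0.02 SD to the detectable difference (1.13 to 1.15), or about 0.03 SD with 10 completers per arm. No new data are needed: blood and stool are already sampled before randomisation and at week 6, and the paired tests already require a baseline for the clinical measures. One point to confirm: pre-randomisation timing is stated only for blood and stool, so the plan should say the same for blood pressure, weight, body fat and sagittal abdominal diameter.
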